7.1.3 RECIST 1.1 Assessment of Disease

RECIST 1.1 will be used by IRR as the primary measure for assessment of tumor response, date of disease progression, and as a basis for all protocol guidelines related to disease status (e.g., discontinuation of study treatment). Although RECIST 1.1 references a maximum of 5 target lesions in total and 2 per organ, this protocol allows a maximum of 10 target lesions in total and 5 per organ, if clinically relevant to enable a broader sampling of tumor burden.

Imaging will be repeated during subsequent treatment/consolidation cycles (between Days 16 to 21), maintenance cycles on Day 77 of each cycle, End-of-Treatment (30 ± 5 days after the last dose of investigational product), and Quarterly Follow-up every 90 (± 14) days for 12 months after the last dose of investigational product or until disease progression. Refer to the study Schedule of Assessments (Section 15.1), as well as in the Procedures: Section 6.3, Section 6.4.3, Section 6.5, and Section 6.6, respectively.

7.1.4 iRECIST Assessment of Disease

iRECIST is based on RECIST 1.1 but adapted to account for the unique tumor response seen with immunotherapeutic drugs. A description of the adaptations and iRECIST process is provided in Section 15.5 with additional details in the iRECIST publication [40]. A summary of imaging and treatment requirements after first radiologic evidence of progression is provided in Table 7 and illustrated as a flowchart in Figure 2.

iRECIST will be used by the investigator to assess tumor response and progression and make treatment decisions. When clinically stable, subjects should not be discontinued until progression is confirmed by the investigator, working with local radiology, according to the rules outlined in Section 15.5, and in consultation with the sponsor's medical monitor. This allowance to continue treatment despite initial radiologic progressive disease takes into account the observation that some subjects can have a transient tumor flare in the first few months after the start of immunotherapy, and then experience subsequent disease response. This data will be captured in the clinical database.

[figure not shown]
Table 7 Imaging and Treatment after First Radiologic Evidence of Progressive Disease

	Clinically Stable		Clinically Unstable	
	Imaging	Treatment	Imaging	Treatment
First radiologic evidence of progressive disease by RECIST 1.1	Repeat imaging at 4 to 8 weeks to confirm progressive disease.	May continue study treatment at the investigator's discretion while awaiting confirmatory tumor imaging by site by iRECIST, see Figure 1^a	Repeat imaging at 4 to 8 weeks to confirm progressive disease per investigator's discretion only.	Discontinue pembrolizumab. May be allowed to be treated with a tabelecleucel product with a different HLA restriction (if available) in consultation with the sponsor's medical monitor, see Figure 1 .
Repeat tumor imaging confirms progressive disease (iCPD) by iRECIST per investigator assessment	No additional imaging required.	Discontinue pembrolizumab (exception is possible upon consultation with Sponsor). May be allowed to be treated with a tabelecleucel product with a different HLA restriction in consultation with the sponsor's medical monitor, see Figure 1 .	No additional imaging required.	Not applicable
Repeat tumor imaging shows iUPD by iRECIST per investigator assessment	Repeat imaging at 4 to 8 weeks to confirm progressive disease. May occur at next regularly scheduled imaging visit.	Continue study treatment at the investigator's discretion, see Figure 1^a	Repeat imaging at 4 to 8 weeks to confirm progressive disease per investigator's discretion only.	Discontinue pembrolizumab. May be allowed to be treated with a tabelecleucel product with a different HLA restriction (if available) in consultation with the sponsor's medical monitor, see Figure 1
Repeat tumor imaging shows iSD, iPR, or iCR by iRECIST per investigator assessment.	Continue regularly scheduled imaging assessments.	Continue study treatment at the investigator's discretion. Refer to Figure 1 for details.	Continue regularly scheduled imaging assessments.	May restart study treatment if condition has improved and/or clinically stable per investigator's discretion. Next tumor imaging should occur according to the regular imaging schedule. Refer to Figure 1 for details.

Table 7 Imaging and Treatment after First Radiologic Evidence of Progressive Disease

	Clinically Stable		Clinically Unstable	
	Imaging	Treatment	Imaging	Treatment
Abbreviations: IRR: Independent Radiographic Review; iCPD: iRECIST confirmed progressive disease; iCR: iRECIST complete response; iRECIST: modified Response Evaluation Criteria in Solid Tumors 1.1 for immune-based therapeutics; iSD: iRECIST stable disease; iUPD: iRECIST unconfirmed progressive disease; RECIST 1.1: Response Evaluation Criteria in Solid Tumors 1.1.				
^a	For a clinically stable subject with first radiographic evidence of progressive disease by RECIST 1.1 (ie, unconfirmed progressive disease), it is at the discretion of the investigator not continue treating the subject with the assigned treatment per protocol until cPD at least 28 days from the date of the scan first suggesting progressive disease. If radiographic progression is not confirmed by iRECIST per the investigator, then the subject may continue on treatment and follow the regular imaging schedule intervals until cPD at a later point by the study site in consultation with the medical monitor.			

Figure 2 Imaging and Treatment for Clinically Stable Subjects Treated with Tabelecleucel and Pembrolizumab after First Radiologic Evidence of Progressive Disease Assessed by the Investigator

7.2 Laboratory Assessments

7.2.1 Local Laboratory Tests

Routine safety laboratory tests will be performed by local laboratories and results from these tests will be reported.

A serum pregnancy test will be performed.

CMV antibody will be collected at the study sites and analysis will be performed by the local laboratory.

The hematology panel will comprise the following parameters: CBC (red blood cells, hematocrit, hemoglobin, white blood cells) with differential (absolute neutrophils, lymphocytes, monocytes, eosinophils, and basophils) and platelets.

The coagulation panel will comprise the following parameters: PT, aPTT, and INR.

[figure not shown]
[figure not shown]
[figure not shown]
The full chemistry panel will comprise the following standard parameters: sodium, potassium, chloride, total carbon dioxide, BUN, creatinine, glucose (fasting), total calcium, albumin, total protein, serum creatinine, TBIL, ALT, AST, alkaline phosphatase, and tests of thyroid function (TSH, T3, and T4).

The abbreviated chemistry panel will consist of serum creatinine, TBIL, ALT, AST, alkaline phosphatase, glucose (fasting) and tests of thyroid function (TSH, T3, and T4).

High resolution HLA typing is comprised of DNA-level data for HLA-A, -B, -C, -DRB1, and -DQB1. Historical high-resolution HLA typing data are acceptable; but if these data are not available, high resolution typing will be performed so that HLA matching can be determined prior to enrollment.

7.2.2 *Central Laboratory Tests*

A tumor/active site core needle, incisional or excisional biopsy is required; fine needle aspirate is not for the purposes of this biopsy; hematology and coagulation panels must be performed prior to biopsy. Subjects for whom a new biopsy cannot be obtained (eg, inaccessible or subject safety concern) may submit an archived specimen only upon agreement from the sponsor. **CCI**

Samples will be collected and shipped to a central laboratory according to the instructions in the Laboratory Manual.

7.2.3 Reporting Routine Laboratory Abnormalities

Laboratory test results along with appropriate normal ranges are to be reported routinely in the appropriate electronic data capture form. In addition, the investigator is responsible for reviewing laboratory test results and determining whether they meet AE reporting criteria (see Section 8), in which case they are to be reported on the adverse event form as well.

8 ADVERSE EVENTS

An AE is any untoward medical occurrence in a patient or clinical investigation subject administered a pharmaceutical product and which does not necessarily have to have a causal relationship with this treatment. An AE can therefore be any unfavorable and unintended sign (eg, an abnormal laboratory value), symptom, or disease temporally associated with the use of the investigational product, whether or not considered related to the investigational product [19].

Out of range laboratory values that are assessed as clinically meaningful per investigator's medical judgement must be reported as AEs with severity grading (see Section 8.3), even if they are asymptomatic. The investigator is responsible for reviewing all laboratory test results (either collected as per protocol or for any other reason) and determining whether an abnormal value in an individual subject is clinically meaningful. When part of a clinical condition, the underlying diagnosis should be listed as the AE in preference to the abnormal laboratory value (eg, anemia rather than low hemoglobin). If a unifying diagnosis is not available, then the sign(s)/symptom(s) must be reported as AE(s) in addition to the laboratory abnormality.

A laboratory value that is determined to be erroneous does not require reporting as an AE; however, any AE resulting from an action taken to treat a subject with an erroneous laboratory value should be reported as such (eg, an adverse reaction or worsening medical condition resulting from any clinical intervention based on the laboratory result).

Investigators must report all AE terms (ie, diseases/diagnoses, symptoms, or signs) and determine their seriousness criteria (Section 8.1) and severity grade (Section 8.3), as well as assess their relationship to the investigational product (Section 8.4).

If an AE changes seriousness criteria or severity grade, that event will be ended and a new AE with the changed seriousness criteria or severity grade will be recorded. Changes to other AE attributes (eg, causality) should be evaluated by the investigator to determine if a new event should be recorded.

Treatment-emergent AEs (TEAEs) are defined as events not present prior to the initiation of study product or any event already present that worsens in either intensity or frequency following exposure to study treatment.

An AE does not include the following:

- Medical or surgical procedures (eg, surgery, endoscopy, dental extraction, transfusion); the condition that necessitates the procedure is the AE

- Any pre-existing disease or condition or laboratory abnormality which is present prior to the start of the study product and that does not worsen
- Situations where an adverse medical event has not occurred (ie, hospitalization for elective surgery, social admission)

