Note: Dosing interruptions are permitted in the case of medical/surgical events or logistical reasons (ie, elective surgery, unrelated medical events, subject vacation, holidays) not related to the administration of investigation product. Subjects should be placed back on the treatment schedule within 3 weeks of the scheduled interruption, unless otherwise discussed with the sponsor's medical monitor. The reason for dose interruption should be documented in the subject's study record.

5.2.2 *Duration of Treatment and Subject Participation*

The duration of treatment is dependent on a subject's response to treatment and is estimated to be approximately 2 years for subjects with a response to treatment (CR, PR, or SD): a maximum of 4 treatment/consolidation cycles (21-day cycles of 3 infusions of tabelecleucel and 1 of pembrolizumab) and maintenance cycles (84-day cycles of 4 infusions of pembrolizumab and

1 of tabelecleucel) until up to a total of 35 pembrolizumab infusions (including for treatment, consolidation, and maintenance) have been given.

After treatment/consolidation and maintenance cycles, subjects will have an End-of-Treatment visit (30 days after the last dose of investigational product) and then enter Quarterly Follow-up for 12 months after the last dose of investigational product. Before receiving any treatment, subjects must undergo a tabelecleucel inventory check and screening, with screening up to 28 days prior to the first dose of investigational product.

5.2.3 *Definition of Dose-limiting Toxicity*

All toxicities will be graded based on the investigator's assessment using CTCAE version 5, except for certain events described in Section 8.3, which have a separate grading system.

The DLT window of observation will be during Treatment Cycle 1 only (ie, during the first 21-day cycle; adverse events (AEs) meeting the definition of a DLT but occurring after this period will not be considered DLTs).

The occurrence of any of the following toxicities during Treatment Cycle 1 will be considered a DLT, if assessed by the investigator to be possibly related or related to investigational product administration (either tabelecleucel and/or pembrolizumab), excluding toxicities clearly not related to the investigational product, such as disease progression, environmental factors, unrelated trauma, etc.:

- Grade 4 nonhematologic toxicity (not laboratory).
- Grade 4 hematologic toxicity lasting ≥ 7 days, except thrombocytopenia:

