 - Grade 4 thrombocytopenia of any duration
 - Grade 3 thrombocytopenia associated with bleeding that requires a platelet transfusion
- Any nonhematologic AE grade ≥ 3 in severity should be considered a DLT, with the following exceptions: grade 3 fatigue lasting ≤ 3 days; grade 3 diarrhea, nausea, or vomiting without use of anti-emetics or anti-diarrheals per standard of care; grade 3 rash without use of corticosteroids or anti-inflammatory agents per standard of care.
- Any grade 3 or grade 4 non-hematologic laboratory value if:
 - Clinically significant medical intervention is required to treat the subject, or
 - The abnormality leads to hospitalization, or
 - The abnormality persists for > 1 week.
 - The abnormality results in a Drug-induced Liver Injury (DILI)
 - Exceptions: Clinically nonsignificant, treatable, or reversible laboratory abnormalities including liver function tests, uric acid, etc.

- Febrile neutropenia grade 3 or grade 4:
 - Grade 3 is defined as ANC < 1000/mm³ with a single temperature of > 38.3 degrees C (101 degrees F) or a sustained temperature of ≥ 38 degrees C (100.4 degrees F) for more than 1 hour
 - Grade 4 is defined as ANC < 1000/mm³ with a single temperature of > 38.3 degrees C (101 degrees F) or a sustained temperature of ≥ 38 degrees C (100.4 degrees F) for more than 1 hour, with life-threatening consequences and urgent intervention indicated.
- Prolonged delay (> 2 weeks) in initiating Cycle 2 due to treatment-related toxicity.
- Any treatment-related toxicity that causes the subject to discontinue treatment during Cycle 1.
- Missing > 25% of pembrolizumab or tabelecleucel doses as a result of investigational product-related AE(s) during the first cycle.
- Grade 5 toxicity.

Any subject experiencing any DLT will be withdrawn from treatment (both investigational products). Whenever possible, protocol-defined follow-up will be continued after the subject has discontinued investigational product treatment (refer to Section 6.7).

MTD definition: The MTD is defined as the highest dose level at which the subject incidence of a DLTs during the first 21-day cycle of investigational product dosing is < 33%.

RP2D definition: The RP2D is no higher than the MTD and is based on optimal benefit-risk, as determined by the SDRC.

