## **11 SAFETY ANALYSES**

### **11.1 Summary of Adverse Events**

MedDRA version 24.0 or later will be used to code AEs to a system organ class (SOC) and a PT within the SOC. The National Cancer Institute Common Terminology Criteria for Adverse Events (CTCAE) version 5.0 will be used to grade severity of AEs. For certain AEs for which CTCAE does not apply, non-CTCAE grades will be applied. The severity grade of non-CTCAE graded AEs are mapped using the following rules and then summarized together with CTCAE graded AEs: mild (grade 1), moderate (grade 2), severe (grade 3), life-threatening (grade 4), or death (grade 5). In addition, for graft-versus-host disease (GvHD), the Center for International Blood and Marrow Transplant Research (CIBMTR) consensus grading system will be used. CIBMTR grading includes an overall grade and separate grades based on rash status, bilirubin level, diarrhea status, and nausea status.

TEAEs are defined as follows:

- Any AE occurring after initiation of the first dose of study treatment through 30 days after the last administration of study treatment or
- Any pre-existing AE (ie, started prior to the first dose of study treatment) that worsened after the first dose through 30 days after the last administration of study treatment or
- Any related AE on or after first dose.

AEs occurring on the same day of the first dose of study treatment will be counted as TEAEs. AEs with complete or partial missing start/end dates will be all considered as treatment-emergent unless

- The partial start date is clearly after the 30 days of the last dose of study treatment. For example, last dose date + 30 days is in November and the AE start date is in the next January with the day missing.

or

- The partial end date is clearly before the first dose date of study treatment. For example, the first dose date is in March while the AE end date is in February with the day missing.

Imputation rules for partial missing dates may be applied to TEAE start/end dates, as described in Section 7.3.

All the AEs collected in this study (whether or not treatment-emergent) will be listed; TEAEs will be summarized as follows:

- Overall Summary of AE including
  - Any TEAEs
  - TEAEs with worst grade  $\geq 3$
  - Fatal TEAEs
  - Serious TEAEs
  - TEAEs leading to any study treatment discontinuation
  - TEAEs leading to any study treatment interruption

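### The SAP's treatment-emergent rule does not link AE records that the protocol splits, so a pre-dose AE that merely improves after dosing is counted as a TEAE

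*Protocol*

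**What the plan says.** **Recording rule (Protocol Section 8).** "If an AE changes seriousness criteria or severity grade, that event will be ended and a new AE" is recorded. The rule has no direction: improvement splits a record just as deterioration does.

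**Protocol definition of a TEAE (Section 8).** Two kinds of event qualify: "events not present prior to the initiation of study product", and "any event already present that worsens in either intensity or frequency following exposure to study treatment". The list of what is not an AE includes "Any pre-existing disease or condition or laboratory abnormality which is present prior to the start of the study product and that does not worsen".

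**SAP definition of a TEAE (Section 11.1).** Three bullets are joined by *or*:
- Bullet 1: "Any AE occurring after initiation of the first dose of study treatment through 30 days after the last administration of study treatment".
- Bullet 2: an AE that began before first dose and worsened after it, within the same 30-day limit.
- Bullet 3: any related AE on or after first dose.

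**Which pre-dose AEs exist as records (Protocol Section 8.5).** Between first consent and first dose, only AEs judged at least possibly related to a study procedure are reported.

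**DLT provisions that depend on duration (Protocol Section 5.2.3).** There are three: "Grade 4 hematologic toxicity lasting ≥ 7 days, except thrombocytopenia"; a grade 3 or 4 non-hematologic laboratory value that persists beyond one week; and the exception for "grade 3 fatigue lasting ≤ 3 days". SAP Section 8.1.1 refers back to Section 5.2.3 and adds no rule for computing duration.

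**The concern.** TEAE tables are built from AE records. Under the recording rule, one clinical event can occupy several records, each with its own start date. A record opened after first dose because a pre-dose event got better looks the same as a new event unless the two parts are linked, and neither document links them.

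The safety profile is a primary endpoint, and the SAP reports it on 12 subjects (SAP Section 1). At that size, one subject wrongly counted under a preferred term is visible in the table. The affected events come from study procedures before any study treatment was given, so they do not belong in a treatment-emergent count.

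**Working it through.** The plan states no figure on this point, so the check is to trace records through the two definitions.

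**Trace for TEAE status.** Take a procedure-related AE recorded before first dose and still present at first dose, such as biopsy-site pain (an assumed example).

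| Course after first dose | New record after first dose? | Protocol Section 8 | SAP 11.1 as written |
|---|---|---|---|
| Grade 2, unchanged | No | Not a TEAE | Not a TEAE |
| Grade 1, rises to grade 2 on Day 3 | Yes | TEAE (worsened) | TEAE (bullet 1) |
| Grade 2, falls to grade 1 on Day 3 | Yes | Not a TEAE | TEAE (bullet 1) |

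The third row is the conflict. The SAP leaves out an event that stays the same and counts one that gets better.

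**Whether bullet 2 prevents this.** It does not. The bullets are alternatives, so bullet 2 can add events but cannot remove one that bullet 1 has admitted. It also covers only AEs that began before first dose, and the new record begins after it.

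**Size.** Inputs: 12 subjects (SAP Section 1); k subjects with an affected event, where k is not given and is an assumption.
- Added incidence = k/12.
- k = 0: 0 points. k = 1: 1/12 = 8.3 points. k = 2: 2/12 = 16.7 points.

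These are upper values. SAP 11.1 tabulates subjects, so a subject who already has a TEAE under the same preferred term adds nothing to that row. The example above adds one grade 1 entry and leaves the grade 3 or higher, serious and fatal rows unchanged.

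The most obvious source of pre-dose procedural events is the screening biopsy in PD-1/PD-L1 failures, of whom at least 6 are required per dose level. Six is not an estimate of k. Protocol Section 6.2 allows an archival sample instead, and a biopsied subject counts only if an event was recorded, was still present at first dose, and then improved. The second biopsy, between Cycle 1 Days 8 and 15, comes after first dose and does not enlarge this pool.

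**Trace for DLT duration (secondary).** With assumed episodes, reading by record and reading by episode give:
- Laboratory value, grade 3 for 5 days then grade 4 for 5 days: 5 + 5 = 10 days, more than 7. Neither 5-day record exceeds 7.
- Grade 4 hematologic toxicity, 4 days non-serious then 4 days serious: 4 + 4 = 8 days, at least 7. Neither 4-day record reaches 7.
- Grade 3 fatigue, 2 days non-serious then 3 days serious: 2 + 3 = 5 days, outside the exception. Each record alone falls within it.
- Grade 4 hematologic toxicity for 6 days, then grade 3: 6 days at grade 4 on either reading, so a grade split changes nothing.

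The two readings can therefore differ. This trace does not show that anyone would use the record-level reading.

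**The case against.** **The definitions already require worsening.** Both documents plainly intend this, and a careful programmer might apply it. The intent is not in doubt. The SAP's wording still does not carry it out, because bullet 1 stands alone and contains no exception for continued events.

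**The effect is small.** This stands. Only procedure-related events are recorded before dosing, few are likely to persist to first dose, and most would be low grade.

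**Linking may be specified elsewhere.** Protocol Section 8.5.1 mentions an eCRF completion guide that is not among the documents, so this cannot be excluded. The TEAE derivation nevertheless belongs in the SAP, which has detailed rules for partial dates and none for split records.

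**The tempting stronger reading.** A reader might infer that splitting hides duration-based DLTs and could have reversed a de-escalation decision, for example by turning 2/6 into 1/6 or 4/12 into 3/12. The documents do not support that:
- Section 5.2.3 words duration on the toxicity or abnormality, not on a record, and the investigator assesses relatedness. No document derives DLT duration from AE record dates.
- Laboratory results are reported separately from the AE form (Protocol Section 7.2.3), so the duration of a laboratory abnormality can be seen without AE records.
- Some events would qualify by routes that do not depend on duration: febrile neutropenia, stopping treatment in Cycle 1 for related toxicity, or missing more than 25% of doses for related AEs (one tabelecleucel dose of three is 33%).
- The SAP says the study ended in Phase 1B with 12 subjects enrolled, and describes the safety committee's review in the past tense (Sections 1 and 2.2). No Cohort 1 dose decision remains to be affected.

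**Conclusion.** The point holds for treatment-emergent status. The protocol's recording rule and SAP 11.1 bullet 1 together count an improving pre-dose event as a TEAE, contrary to the protocol's definition. This rests on reading bullet 1 by record start date, which is how it is worded, and on there being no linking rule outside these documents.

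The size is at most 8.3 points per affected subject in a 12-subject incidence. The number affected is unknown but probably small, and the added events are mostly low grade. It is worth correcting because the safety profile is a primary endpoint and the correction is cheap. It does not threaten the overall safety conclusion.

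For DLTs, all that remains is that the SAP does not say how a duration is counted across split records. That calls for a clarifying sentence; it is not evidence of an under-count.

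**What to change.** In SAP Section 11.1:

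1. Link contiguous records of the same event (same term, the next record starting where the previous one ended) into one episode.
2. Apply bullet 1 only to episodes with no pre-dose record.
3. Call an episode with pre-dose onset treatment-emergent only if, after first dose, it worsens in intensity (grade or seriousness) or in frequency, or if it qualifies as related under bullet 3. A comparison of grades alone would not be enough: it would drop worsening in frequency, which the protocol includes, and would override bullet 3. Treating a move to serious as worsening should be stated explicitly, because Protocol Section 8.1.1 separates seriousness from severity.
4. As a clarification, state that for the reported DLT incidence each duration in Protocol 5.2.3 is read over the linked episode, across seriousness and grade splits, within the grades that the criterion names. Grade 3 and grade 4 days are thus taken together for the laboratory criterion of more than one week, and grade 4 days only for the hematologic criterion.

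The cost is a few lines of text and one programming step on data already collected. TEAE counts may be slightly lower as a result.
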